#### Subject Identification, Recruitment And Consent/Assent

At roadway intersections in close proximity to the [name] Chiropractic Clinic signage will be erected containing the verbiage: "Weight Loss Clinical Study, 40 Participants, [contact]" in order to recruit study volunteers from the community.

The clinic's patients will be provided an opportunity to volunteer for consideration as a trial participant.

The primary investigator will conduct all subject interviews and obtain informed consent. A thorough disclosure of all clinical process, contraindications, and any risk will be discussed with candidates for the trial.

All candidates will be older than the age of majority in the state of Tennessee (18 years old) but none shall be older than 65 years of age.

No candidates of diminished capacity will be considered for inclusion in the trial.

Capacity is a functional assessment and a clinical determination about a specific decision that can be made by any clinician familiar with a patient's case. The four key components addressed during the candidates capacity evaluation include: 1) communicating a choice, 2) understanding, 3) appreciation, and 4) rationalization/reasoning.

There shall be no cost incurred by candidates for inclusion in the study or individuals selected to participate in the study.

No monetary remuneration will be offered participants in the study. However an offer will be made "post blind" to the participants who received treatment using the sham device for an additional nine (9) sessions of treatments using a fully functional invisa-RED Technology Elite device. This offer will provide the participants treated with the sham device the opportunity to benefit from the weight loss and aesthetics therapy.

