## **Criteria for Participants**

The number of participants is projected to be forty (40).

There will be an equitable distribution of male and female participants.

Women who are pregnant, trying to get pregnant, or nursing will be excluded from the study, as they should not receive Low-level Laser Therapy (LLLT). There is no evidence of harm to a an unborn baby however there have been no safety tests either, so for medical legal reasons we recommend never treating such individuals.

The participants will be between the ages of 18-65 years.

The ethnicity of the participants will be equitably distributed.

Inclusion criteria will be individuals that may benefit from a weight loss therapy.

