## Exclusion criteria will include the following:

- If you are pregnant, trying to get pregnant or nursing laser light therapy should be received only after the end of these conditions. There is no evidence of harm to a an unborn baby however there have been no safety tests either, so for medical legal reasons we recommend never treating areas directly over a developing child.
- Individuals with hypertension, light sensitive epilepsy, cancer, heart disease, infectious skin disease, and severe varicose veins should not use this device.
- People suffering from infectious and acute disease such as a fever should not use this device.
- People who have hemorrhagic disease, vascular ruptures, skin inflammation, or any disease of the skin should not use this device.
- People who have immune system dysfunction such as Leukemia, Hemophilia, etc., and light sensitive persons should not use this device.
- Individuals with a history of melanoma, raised moles, suspicious lesions, keloid scar formation, or healing problems should not undergo laser light therapy.
- Individuals with active infections, open lesions, hives, herpetic lesions, cold sores, or tattoos and permanent make-up in the area of treatment should not undergo laser light therapy.
- People who have used isotretinoin (commonly known as Accutane), tetracycline, St. John's Wort, or any photo sensitizing drugs in the last year should not undergo laser light therapy.
- Individuals with autoimmune diseases such as Lupus, Scleroderma, or Vitiligo should not undergo laser light therapy.
- Individuals who have pacemakers or other electro-stimulation devices surgically implanted should not undergo laser light therapy.
- Any insulin dependent individual should consult their physician before undergoing laser light therapy.
- All individuals considered "vulnerable" such as children, pregnant women, nursing home residents or other institutionalized persons, students, employees, fetuses, prisoners, and persons with decisional incapacity.

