#### **Methods and Procedures**

The trial is designed to prove the efficacy and safety of the invisa-RED Technology Elite Low-level Laser Therapy (LLLT) device. The trial will compare results between two groups; the first will be treated using a fully functional invisa-RED Technology Elite device; this group will be internally designated the Usual Care Group. The second, a control group, will be treated utilizing a nonfunctional invisa-RED Technology Elite device; this group will be referred to internally as the Sham Group.

The sham device will consist of an invisa-RED Technology Elite device that will appear to operate as the Usual Care Group device to the operator, but the laser diodes will be disabled and will receive no power. If staff or a participant questions the efficacy of the sham device, an assertion may be made that only a near infrared, nonvisible frequency of light, is being employed.

The trial will be conducted employing a double blind study methodology; participants will be randomly assigned to each group through a drawing, neither participants nor clinicians will know to which trial group they are assigned. To ensure the double blind; treatment for the two groups will occur on separate days of the week. All participants will receive therapy at the [name] Chiropractic Center located in Hixson, TN. Group 1 will be assigned Monday, Wednesday, Friday, and Group 2; Tuesday, Thursday, and Saturday. Additionally staff administering the trial therapy will be assigned to work with one (1) group exclusively.

A simplified weight loss protocol will be employed based on the "Consultation Protocol" from the invisa-Red Training Manual. All study participants will undergo nine (9) therapy sessions of 20 minutes each; using a singular protocol setting for pulse (3.5s) and delay (0.2s), but power settings will be based on the participants Fitzpatrick Scale skin type. For skin types i and ii a power setting of 7 will be used, for skin types iii and iv a power setting of 6, for skin types v and vi a power setting of 4 will be employed. At the conclusion of the nine (9) therapy sessions; the change in body fat percentage, weight, and inches lost of the two groups will be statistically analyzed to determine the efficacy of the invisa-RED Technology Elite as a weight loss therapy. Any medical errors will be included in the statistical analysis.

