- Use of laser light therapy in the ears, nose, eye, or throat is not recommended.
- Individuals with a history of melanoma, raised moles, suspicious lesions, keloid scar formation, or healing problems should not undergo laser light therapy.
- Individuals with active infections, open lesions, hives, herpetic lesions, cold sores, or tattoos and permanent make-up in the area of treatment should not undergo laser light therapy.
- People who have used isotretinoin (commonly known as Accutane), tetracycline, St. John's Wort, or any photo sensitizing drugs in the last year should not undergo laser light therapy.
- Individuals with autoimmune diseases such as Lupus, Scleroderma, or Vitiligo should not undergo laser light therapy.
- Individuals who have pacemakers or other electro-stimulation devices surgically implanted should not undergo laser light therapy.
- Any insulin dependent individual should consult their physician before undergoing laser light therapy.

All prospective participants interviewed for the trial will be vetted using the invisaRED Technologies Elite guidelines of indications and contraindications. Upon following all guidelines for indications and contraindications and employing both standard procedures for eye safety and treatment protocols, a participant's risk may best be compared to exposure to direct sunlight.

Subjects of the study receiving the invisaRED Technologies Elite therapy may receive the following health and aesthetic benefits:

- Body fat reduction through laser assisted lipolysis or \*photobiostimulation which has been shown to increase cellular metabolism
- Sculpting of targeted body areas through adipose tissue reduction and skin tightening.
- Stretch mark fading
- Elimination or reduction of cellulite
- Skin tightening and enhanced collagen production
- Increase blood flow to areas of epidermis, dermis, hypodermis, and connective tissue to stimulate cellular respiration
- Detoxification due to improved blood circulation and stimulation of lymphatic transport.

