Null Hypothesis Three (3): There is not a statistically significant difference in Pounds of Body Fat Lost when using an invisa-RED Technology Elite Low-level Laser Therapy (LLLT) device when compared with a sham (placebo) device as a therapy in an approved and standardized clinical protocol.

Alternative Hypothesis Three (3): There is a statistically significant difference in Pounds of Body Fat Lost when using an invisa-RED Technology Elite Low-level Laser Therapy (LLLT) device when compared with a sham (placebo) device as a therapy in an approved and standardized clinical protocol.

Data Sets/Populations:

Criteria for Participants:

Participants will be taken from a random population of respondents to both email and social media recruitment. The number of participants is projected to be forty (40). There will be an equitable distribution of male and female participants. Women who are pregnant, trying to get pregnant, or nursing will be excluded from the study, as they should not receive Low-level Laser Therapy (LLLT). Note; there is no evidence of harm to an unborn baby however there have been no safety tests either, so for medical legal reasons we recommend never treating such individuals. The participants will be between the ages of 18-75 years. Inclusion criteria will be individuals that may benefit from a weight loss therapy.

Exclusion criteria will include the following:

- If you are pregnant, trying to get pregnant or nursing laser light therapy should be received only after the end of these conditions. There is no evidence of harm to an unborn baby however there have been no safety tests either, so for medical legal reasons we recommend never treating areas directly over a developing child.
- Individuals with hypertension, light sensitive epilepsy, cancer, heart disease, infectious skin disease, and severe varicose veins should not use this device.
- People suffering from infectious and acute disease such as a fever should not use this device.
- People who have hemorrhagic disease, vascular ruptures, skin inflammation, or any disease of the skin should not use this device.
- People who have immune system dysfunction such as Leukemia, Hemophilia, etc., and light sensitive persons should not use this device.
- Individuals with a history of melanoma, raised moles, suspicious lesions, keloid scar formation, or healing problems should not undergo laser light therapy.

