- Individuals with active infections, open lesions, hives, herpetic lesions, cold sores, or tattoos and permanent make-up in the area of treatment should not undergo laser light therapy.
- People who have used isotretinoin (commonly known as Accutane), tetracycline, St. John's Wort, or any photo sensitizing drugs in the last year should not undergo laser light therapy.
- Individuals with autoimmune diseases such as Lupus, Scleroderma, or Vitiligo should not undergo laser light therapy.
- Individuals who have pacemakers or other electro-stimulation devices surgically implanted should not undergo laser light therapy.
- Any insulin dependent individual should consult their physician before undergoing laser light therapy.
- All individuals considered "vulnerable" such as children, pregnant women, nursing home residents or other institutionalized persons, students, employees, fetuses, prisoners, and persons with decisional incapacity.

From the population of prospective participants screened using the above criteria, each of the approximately 40 participants selected will be randomly assigned to one of two groups; the Care as Usual Group or the Sham (placebo) Group.

Analysis:

To examine the three (3) research questions, independent sample *t*-tests using the statistical analysis program SPSS will be conducted on the three comparative data sets. Each of the three data sets will be comprised of comparative results from the two trial groups, the Care as Usual Study Group and the Sham (placebo effect) Study Group.

Data set One (1) will be the comparative Percentage of Body Fat Lost results, Data Set Two (2) will be the comparative Inches Lost results, and Data Set Three (3) will be the comparative Weight of Body Fat Lost results.

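### Clinic patients may enrol with no exclusion for, or record of, earlier low-level laser treatment, and any who have had it might recognise the unpowered sham

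*Protocol*

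**What the plan says.** **Who can enter.** The protocol (Subject Identification, Recruitment And Consent/Assent) recruits by road signs near the treating clinic and adds that "The clinic's patients will be provided an opportunity to volunteer for consideration as a trial participant". The SAP (Data Sets/Populations) gives a different route: "Participants will be taken from a random population of respondents to both email and social media recruitment". It does not mention clinic patients.

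**Eligibility.** The only positive criterion beyond age is broad: "Inclusion criteria will be individuals that may benefit from a weight loss therapy". The exclusion lists in the protocol and SAP cover diseases, skin conditions, drugs, implants, pregnancy and vulnerable persons. The one look-back on an earlier exposure concerns medicines: "People who have used isotretinoin (commonly known as Accutane), tetracycline, St. John's Wort, or any photo sensitizing drugs in the last year". The protocol's Risk/Benefit Assessment adds that "All prospective participants interviewed for the trial will be vetted using the invisaRED Technologies Elite guidelines of indications and contraindications". The contraindications listed there do not mention earlier laser treatment either.

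**Sham and blind.** Under Methods and Procedures, the sham is an invisa-RED Elite in which "the laser diodes will be disabled and will receive no power", and the blinding claim is that "neither participants nor clinicians will know to which trial group they are assigned". The same section puts the two groups on different weekdays, assigns each staff member to one group only, and supplies a reply about invisible light in case the sham is doubted.

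**Analysis.** Both documents specify independent-samples t-tests, with no covariate, no stratification and no check of blinding.

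**The concern.** A sham-controlled trial of weight, fat and inches lost relies on participants not knowing their arm, because these outcomes can respond to diet and motivation. A person who has never had laser treatment has nothing to compare the sham with. A person who has had it does, and the scripted explanation is likely to be least convincing to that person. The plan opens enrolment to the treating clinic's patients without asking whether they have had such treatment.

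The schedule raises the stakes. Everyone attending on a given day has the same allocation. If one participant concludes that the device is inactive and says so, others in that group, and the staff who work only with it, can infer their own arm. The other group's arm follows by elimination. A resulting change in behaviour would appear as a difference between groups that the device did not cause.

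**Working it through.** The plan gives no figure to reproduce on this point. Its stated sample size of 40 comes without an effect size, standard deviation (SD), power or allocation ratio. The check is therefore mainly a comparison of texts.

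**Step 1. Is earlier laser treatment covered anywhere?**

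| Place | Covers earlier laser treatment? |
|---|---|
| Protocol, Criteria for Participants | No |
| Protocol, exclusion criteria | No; the only look-back is for photosensitising drugs, one year |
| Protocol, Risk/Benefit Assessment (contraindications used for vetting) | No |
| SAP, Criteria for Participants and exclusion criteria | No |
| Protocol and SAP, analysis sections | Not recorded, stratified or adjusted for |

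**Step 2. Could an experienced participant tell the devices apart?** Cues for: the sham diodes are unpowered; the Risk/Benefit Assessment says Class 3B lasers are able to heat skin; and Methods and Procedures promises that the sham will look operational to the operator, with no matching statement about what the participant sees or feels. Cues against: paddles are in place before activation, protective eyewear is recommended, and a reply to doubts is scripted. Recognition is possible but not established.

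**Step 3. How easily could at least one such person be in the sham group?** Assume 20 per group (equal split of 40) and an assumed share p of recruits with earlier treatment. P(at least one) = 1 − (1 − p)^20.

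- p = 0: 0
- p = 5%: 1 − 0.95^20 = 64%
- p = 10%: 1 − 0.90^20 = 88%
- p = 25%: 1 − 0.75^20 = 99.7%

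The documents give no value for p.

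**Step 4. What could recognition do to a test?** Suppose a share f of the sham group recognises the device and the outcome of those people shifts by b SD. The false difference is f × b SD. With 20 per group, the chance that one two-sided 5% t-test rejects when the device does nothing is the noncentral-t rejection probability on 38 degrees of freedom, with noncentrality f × b × √(20/2).

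| f | b (SD) | False difference (SD) | Rejection probability |
|---|---|---|---|
| 10% | 0.5 | 0.05 | 5.3% |
| 10% | 1.0 | 0.10 | 6.1% |
| 25% | 1.0 | 0.25 | 12% |
| 50% | 1.0 | 0.50 | 34% |

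Both f and b are assumptions. The low rows correspond to a few isolated individuals. The higher rows need either many experienced recruits or recognition spreading through the group. The table shows how a false difference would pass through the test; it does not estimate what this trial would see.

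**Step 5. Carry-over.** Earlier treatment precedes randomisation, so its expected effect is the same in both arms. With 40 people it mainly adds noise or chance imbalance.

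**The case against.** The strongest reply is that the harm needs a fact the documents do not supply: that some volunteers have already had this kind of treatment. A reader might infer routine use at the clinic from the names of the arms, which the SAP gives as "the Care as Usual Group or the Sham (placebo) Group". The text does not support that. The protocol introduces its version of the name as an internal label for the active arm, says only that trial therapy will be given at the clinic, and has a training section under which all trial staff are still to be trained and certified. That fits first use at least as well as established use. This objection stands: the number of experienced participants may be zero.

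A reader might also infer that an experienced participant would identify the sham at the first session. The documents do not support that either. Paddle placement and eyewear limit what can be seen, and nothing says that warmth is felt at the trial's settings.

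A third tempting reading is that carry-over from earlier sessions biases the comparison. It does not do so systematically, because it arises before allocation.

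Finally, if the sham gives detectable cues, newcomers may suspect it too, and the separate days and dedicated staff affect all 40 participants regardless of history. That is true, and an exclusion criterion would not cure it. It does not remove the gap in eligibility, which is real in both documents and costs little to close.

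**Conclusion.** The point holds as a minor one, worth considering. Neither document excludes or records earlier low-level laser treatment, although the protocol invites the treating clinic's own patients. If any experienced people enrol, they might recognise the sham, the day and staff arrangement could spread that knowledge, and the planned t-tests would not reveal or correct it.

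The size of any bias cannot be derived. It depends on the number of experienced recruits, the chance of recognition and the resulting change in outcome, none of which the documents give. The percentages above are illustrations under stated assumptions, including an equal split of 40, and the range begins at no effect. The main ground for action is the threat to the blind; carry-over is secondary. The conflict between the two recruitment descriptions matters here because it leaves unclear how many clinic patients could enter at all.

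**What to change.** 1. Add one line to the exclusion lists of both the protocol and the SAP: *any previous treatment with an invisa-RED device or other low-level laser or light therapy for fat loss or body contouring*.
2. Ask the question at the interview that the investigator already conducts with every candidate, and for clinic patients check the answer against the clinic record.
3. Reconcile the recruitment routes, so that the protocol (road signs and clinic patients) and the SAP (email and social media) describe the same source population.

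The cost is one criterion, one screening question and a record check. The downside is the loss of any volunteers who have already had such treatment; if there are none, nothing is lost.

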### **Requirements for Human Subject Protection Training**

The Primary Investigator and clinical associates conducting the trial will complete the Collaborative Institutional Training Initiative (CITI) course GCP for Clinical Trials with Investigational Drugs and Medical Devices (U.S. FDA Focus).

Statistical Analysis Plan

Cover Page

for the Clinical Study

"Comparing the Efficacy of a Dual-Frequency Laser-Emitting Device, the "invisared-RED Elite", With a Sham Device as Therapy for the Loss of Adipose Tissue (Body Fat) and Aesthetics in Overweight Individuals"

NCT03811093

May 7, 2019

Statistical Analysis Plan

for

Invisa-RED Clinical Trial

Research Questions:

Research Question One (1): Is there a statistically significant difference in Percentage of Body Fat Lost when using an invisa-RED Technology Elite Low-level Laser Therapy (LLLT) device when compared with a sham (placebo) device in an approved and standardized clinical protocol?

Null Hypothesis One (1): There is not a statistically significant difference in Percentage of Body Fat Lost when using an invisa-RED Technology Elite Low-level Laser Therapy (LLLT) device when compared with a sham (placebo) device as a therapy in an approved and standardized clinical protocol.

Alternative Hypothesis One (1): There is a statistically significant difference in Percentage of Body Fat Lost when using an invisa-RED Technology Elite Low-level Laser Therapy (LLLT) device when compared with a sham (placebo) device as a therapy in an approved and standardized clinical protocol.

Research Question Two (2): Is there a statistically significant difference in Inches Lost when using an invisa-RED Technology Elite Low-level Laser Therapy (LLLT) device when compared with a sham (placebo) device in an approved and standardized clinical protocol?

Null Hypothesis Two (2): There is not a statistically significant difference in Inches Lost when using an invisa-RED Technology Elite Low-level Laser Therapy (LLLT) device when compared with a sham (placebo) device in an approved and standardized clinical protocol.

Alternative Hypothesis Two (2): There is a statistically significant difference in Inches Lost when using an invisa-RED Technology Elite Low-level Laser Therapy (LLLT) device when compared with a sham (placebo) device in an approved and standardized clinical protocol.

Research Question Three(3): Is there a statistically significant difference in Pounds of Body Fat Lost when using an invisa-RED Technology Elite Low-level Laser Therapy (LLLT) device as a therapy when compared with a sham (placebo) device in an approved and standardized clinical protocol?

Null Hypothesis Three (3): There is not a statistically significant difference in Pounds of Body Fat Lost when using an invisa-RED Technology Elite Low-level Laser Therapy (LLLT) device when compared with a sham (placebo) device as a therapy in an approved and standardized clinical protocol.

Alternative Hypothesis Three (3): There is a statistically significant difference in Pounds of Body Fat Lost when using an invisa-RED Technology Elite Low-level Laser Therapy (LLLT) device when compared with a sham (placebo) device as a therapy in an approved and standardized clinical protocol.

Data Sets/Populations:

Criteria for Participants:

Participants will be taken from a random population of respondents to both email and social media recruitment. The number of participants is projected to be forty (40). There will be an equitable distribution of male and female participants. Women who are pregnant, trying to get pregnant, or nursing will be excluded from the study, as they should not receive Low-level Laser Therapy (LLLT). Note; there is no evidence of harm to an unborn baby however there have been no safety tests either, so for medical legal reasons we recommend never treating such individuals. The participants will be between the ages of 18-75 years. Inclusion criteria will be individuals that may benefit from a weight loss therapy.

Exclusion criteria will include the following:

- If you are pregnant, trying to get pregnant or nursing laser light therapy should be received only after the end of these conditions. There is no evidence of harm to an unborn baby however there have been no safety tests either, so for medical legal reasons we recommend never treating areas directly over a developing child.
- Individuals with hypertension, light sensitive epilepsy, cancer, heart disease, infectious skin disease, and severe varicose veins should not use this device.
- People suffering from infectious and acute disease such as a fever should not use this device.
- People who have hemorrhagic disease, vascular ruptures, skin inflammation, or any disease of the skin should not use this device.
- People who have immune system dysfunction such as Leukemia, Hemophilia, etc., and light sensitive persons should not use this device.
- Individuals with a history of melanoma, raised moles, suspicious lesions, keloid scar formation, or healing problems should not undergo laser light therapy.

- Individuals with active infections, open lesions, hives, herpetic lesions, cold sores, or tattoos and permanent make-up in the area of treatment should not undergo laser light therapy.
- People who have used isotretinoin (commonly known as Accutane), tetracycline, St. John's Wort, or any photo sensitizing drugs in the last year should not undergo laser light therapy.
- Individuals with autoimmune diseases such as Lupus, Scleroderma, or Vitiligo should not undergo laser light therapy.
- Individuals who have pacemakers or other electro-stimulation devices surgically implanted should not undergo laser light therapy.
- Any insulin dependent individual should consult their physician before undergoing laser light therapy.
- All individuals considered "vulnerable" such as children, pregnant women, nursing home residents or other institutionalized persons, students, employees, fetuses, prisoners, and persons with decisional incapacity.

From the population of prospective participants screened using the above criteria, each of the approximately 40 participants selected will be randomly assigned to one of two groups; the Care as Usual Group or the Sham (placebo) Group.

Analysis:

To examine the three (3) research questions, independent sample *t*-tests using the statistical analysis program SPSS will be conducted on the three comparative data sets. Each of the three data sets will be comprised of comparative results from the two trial groups, the Care as Usual Study Group and the Sham (placebo effect) Study Group.

Data set One (1) will be the comparative Percentage of Body Fat Lost results, Data Set Two (2) will be the comparative Inches Lost results, and Data Set Three (3) will be the comparative Weight of Body Fat Lost results.

An independent samples *t*-test is the appropriate statistical test when the purpose of research is to assess if differences exist on a continuous (interval/ratio) dependent variable by a dichotomous (2 groups) independent variable. The three continuous dependent variables to be tested are Percentage of Body Fat Lost or Gained, Weight of Body Fat Lost or Gained, and Total Inches Lost or Gained. The dichotomous independent variables for the three data sets are the invisa-RED Technology Elite Low-level Laser Therapy (LLLT) device and the sham (placebo) device, each administered as therapy in a standardized clinical protocol. The assumptions of normality and homogeneity of variance will be assessed. Normality assumes that the scores are normally distributed (bell-shaped) and will be assessed using the One-Sample Kolmogorov-Smirnov test. Homogeneity of variance assumes that both groups have equal error variances and will be assessed using Levene's Test for the Equality of Error Variances.

Each t-test will be two- tailed with the probability of rejecting the null hypothesis when it is true set at $p < 0.05$. This ensures a 95% certainty that the differences did not occur by chance. *The first t-test* using Data Set One (1) will assess if statistically significant differences exist on the dependent variable Percentage of Body Fat Lost. The second *t-test* conducted on Data Set Two (2) will assess if statistically significant differences exist on the dependent variable Inches Lost. The third *t-test* conducted on Data Set Three (3) will assess if statistically significant differences exist on the dependent variable Weight of Body Fat Lost. For each of the three data sets the independent variables are defined as an Invisia-RED Technology Elite Low-level Laser Therapy (LLLT) device and as a comparator the sham (placebo) device. Data produced by both groups will be a result of a clinical trial governed and conducted by a randomized double-blind study using an approved clinical protocol.

Reference:

Statistics Solutions. (2013). Data analysis plan: Independent Sample t-Test [WWW Document]. Retrieved from <http://www.statisticssolutions.com/academic-solutions/member-resources/member-profile/data-analysis-plan-templates/data-analysis-plan-independent-sample-t-test/>
